10.7. Biomarker Data

Exploratory biomarker data may be described in a separate exploratory analysis plan. Analyses may include (but are not limited to) evaluating relationships between biomarkers and clinical responses. Exploratory biomarker variables may include (but are not limited to) serum allergenspecific IgE levels (birch, Bet v 1, Bet v 2, and other common allergens) and basophil activation. Relevant biomarker data analyses may be included in the CSR and/or a separate biomarker report.

11. **DATA CONVENTIONS**

11.1. **Definition of Baseline for Efficacy/Safety Variables**

Unless otherwise specified, the Baseline assessment for all measurements will be the latest available valid measurement taken prior to the administration of investigational product. The following rules specify the determination of baseline by both date/time information:

• The date and time of first injection will be used to determine the baseline for the AE, lab, PK and ADA data.

Date: May 31, 2023

• Only the date of first injection will be used to determine the baseline for other data except the AE, lab, PK and ADA data.

For the efficacy endpoints, the baseline is defined as following:

- For all symptom scores (TNSS or TOSS) collected in EEU chambers, the baseline is defined as the mean of the corresponding measurements (2 to 6 hours) during the allergen EEU challenge in screening period. The baseline visit for Birch is Visit 2, and the baseline visit for Oak is Visit 3.
- For daily e-diary scores (daily TNSS, daily TOSS, DMS, daily TSS, daily CSMS, RQLQ(S), PFASQ, and outdoor questionnaire), there are two baselines defined, pretreatment baseline and pre-season baseline.
 - The pre-treatment baseline is defined as the average of the daily score during the screening period before the first dose. All days with scores during the screening period will be used to calculate the average, except for the day of and one day following EEU challenge.
 - The pre-season baseline is defined as the average of the daily score start from the Visit 10 to the day before the local BPS, except for the day of and one day following EEU challenge.

The number of non-missing daily records must be at least 3 after excluding the records happening on the same day and the next day of the EEU visit for pre-treatment and preseason baseline (both pre-treatment baseline) calculation. If the baseline value is smaller than 1, the baseline will be set to 1.

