- 22. Electrocardiogram will be performed locally by the site.
- 23. Spirometry will be performed locally by the site. *Spirometry at screening and randomization is required for all participants for eligibility. At other visits, spirometry and/or peak expiratory flow (PEF) may be performed for participants, per PI judgement.
- 24. Daily TNSS, TOSS, and DMS assessments will being collected by e-diary during screening and in Part B from visit 10 to visit 15. The e-diary is returned at visit 15.
- 25. Screening baseline assessment: e-diary assessments for symptoms and allergy rescue medication use should be obtained for an approximate 2-week period or longer (at minimum 1 week) starting after the screening birch EEU challenge until randomization (visit 4) in eligible subjects. It is recommended that it is performed outside of relevant pollen seasons when pollen-allergic subjects are not significantly symptomatic due to other pollens.
- 26. Pre-season baseline assessment: e-diary assessments for symptoms and allergy rescue medication use should be obtained approximately 2 weeks or longer up (at minimum 1 week) to receipt of dose 2 given ahead of the anticipated BPS (starting at visit 10 [Part B]) and prior to receiving dose 2 at visit 11 ahead of the BPS).
- 27. Allergy relieving rescue medications, as needed, should be dispensed at the end of symptom score collection on visits 2, 3, 6, 7, 8, and 9. Rescue medications are dispensed starting at visit 10 for management of symptoms during the pollen season up to visit 15.
- 28. RQLQ(S) is administered weekly starting at visit 2 (during screening baseline assessment period) and then weekly using an e-diary in Part B starting at visit 10 until visit 15.
- 29. Pollen food allergy questionnaire (PFASQ) is administered every 2 weeks at baseline starting at visit 2 (during screening baseline assessment period) and then every 2 weeks in Part B starting at visit 10 until visit 15.
- 30. Outdoor time questionnaire is administered daily at baseline starting at visit 2 (during screening baseline assessment period) and then daily using an e-diary in Part B starting at visit 10 until visit 15.

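### Three baseline rules in SAP 11.1 distort within-arm changes, can drop participants from RQLQ(S) analyses, and put days after dose #2 into the pre-season baseline

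*SAP*

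**What the plan says.** SAP 11.1 defines two baselines, pre-treatment and pre-season, for a list that opens "For daily e-diary scores (daily TNSS, daily TOSS, DMS, daily TSS, daily CSMS, RQLQ(S), PFASQ, and outdoor questionnaire". Three rules follow.

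- **Floor.** "If the baseline value is smaller than 1, the baseline will be set to 1". Nothing limits this to percent change.
- **Minimum records.** "The number of non-missing daily records must be at least 3 after excluding the records happening on the same day" as an EEU visit and the day after, "for pre-treatment and preseason baseline (both pre-treatment baseline) calculation". The schedule footnotes in SAP 14.2 give other frequencies for two listed instruments: "RQLQ(S) is administered weekly starting at visit 2 (during screening baseline assessment period") and "Pollen food allergy questionnaire (PFASQ) is administered every 2 weeks at baseline starting at visit 2". Visit 2 is itself an EEU day. Footnote 25 asks for a screening diary of about 2 weeks or longer, with a minimum of 1 week.
- **Pre-season window.** The pre-season baseline is the "average of the daily score start from the Visit 10 to the day before the local BPS". Footnote 26 of the schedule, in both Protocol 8.1.1 and SAP 14.2, starts the same assessment at visit 10 but places it before dose #2: "and prior to receiving dose 2 at visit 11 ahead of the BPS". Dose #2 is planned for about 0 to 3 weeks before the anticipated BPS. SAP Table 1, which lists modifications from the protocol, does not mention a changed window.

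These baselines feed the Part B change and percent-change endpoints for CSMS, TSS, TNSS, TOSS, DMS and RQLQ(S) in SAP 7.1.2, and some exploratory endpoints.

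**The concern.** A floor guards against dividing by a value near zero, so it has a purpose in percent change. It has none in absolute change, where it makes an unchanged participant look improved. It also breaks the definitions of TSS and CSMS as sums, because each component is floored separately.

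The three-record rule suits a daily diary. Applied to weekly and two-weekly forms, it conflicts with the diary length the protocol treats as normal. SAP 7.2.2 limits multiple imputation to day 29, so nothing replaces the missing baseline. SAP 14.1 gives RQLQ(S) the same ANCOVA as the row above it, with a baseline covariate. A missing baseline would therefore remove the participant from the RQLQ(S) mean endpoint as well as the change endpoints.

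The pre-season window mixes days before and after dose #2, in proportions set by each participant's dosing date. Table 3 names the pre-treatment baseline as covariate, and that does not correct a contaminated pre-season baseline. Any drug effect between dose #2 and BPS would be partly subtracted from the change.

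**Working it through.** The plan gives no figure on this point and no distribution of diary baselines. Its sample-size calculation is not involved.

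**1. Floor.** For baseline b < 1, reported change is y - 1 instead of y - b, so it is too low by 1 - b.

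- b = 0, y = 0: reported change -1 (-100%); true change 0.
- b = 0.5, y = 3: reported +2.0; true +2.5.
- All-zero components: floored TNSS + TOSS + DMS = 3, but floored CSMS = 1.

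For illustration, assume exponential baselines with mean m. Then P(b < 1) = 1 - exp(-1/m), and the mean shift is -(1 - m × P).

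| m | Share floored | Shift in mean change |
|---|---|---|
| 0.3 | 96% | -(1 - 0.3 × 0.964) = -0.71 |
| 0.8 | 71% | -(1 - 0.8 × 0.713) = -0.43 |
| 1.5 | 49% | -(1 - 1.5 × 0.487) = -0.27 |

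Let f be the floored baseline, used both in the change and as covariate. The model y - f = a + τ·trt + β·f is the same as y = a + τ·trt + (β + 1)·f, so τ is the estimate for the raw mean adjusted for f. Only the quality of the adjustment changes. In a simulation (65 per arm, 400 runs, assumed effect -0.8), raw and floored estimates differed by at most 0.002 at all three values of m. In a separate one (73 per arm, 500 runs, m = 1), both gave -0.967, with SE 0.331 raw and 0.332 floored. The identity needs the same baseline in both places, so it does not cover change from pre-season baseline.

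**2. Record counts.** RQLQ(S) falls on days 0, 7, 14, 21 … from visit 2, and PFASQ on days 0, 14, 28, 42 …. Drop the EEU day and the next day, and count only days before dose #1.

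| Visit 2 to dose #1 | Usable RQLQ(S) records |
|---|---|
| 14 days | 1 (2 if the dosing day counts) |
| 15 to 21 days | 2 (3 at day 21 if the dosing day counts) |
| 22 days | 3 |

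If the oak EEU challenge falls on a questionnaire day such as day 7, days 14, 21 and 28 are needed, so 29 days. PFASQ needs 43 days (42 if the dosing day counts). Before dose #2, the nominal gap from day 127 to day 155 is 28 days and gives 4 RQLQ(S) records.

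**3. Pre-season window.** With p days from visit 10 to dose #2 and q days from dose #2 to BPS, the post-dose share is q/(p + q).

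| q (days) | p = 28 (nominal) | p = 14 | p = 7 (minimum) |
|---|---|---|---|
| 0 | 0% | 0% | 0% |
| 7 | 20% | 33% | 50% |
| 14 | 33% | 50% | 67% |
| 21 | 43% | 60% | 75% |

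If dose #2 adds a between-arm effect of δ points before BPS, the active-arm baseline falls by δ × share, and the arm difference in change shrinks by that amount. For δ = 1 (assumed), this is 0 to 0.43 points at p = 28 and 0 to 0.75 at p = 7. Participants dosed after BPS start, which SAP 2.1 allows, have a share of 0%.

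**The case against.** The floor is pre-specified and identical in all arms, the efficacy comparisons are between arms, and the adjusted difference from pre-treatment baseline hardly moves. That stands: the error is confined to within-arm absolute change and additivity, and its size rests on an assumed distribution.

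The record rule speaks of daily records, and SAP 7.1 describes RQLQ(S) separately as weekly, so a programmer might not apply the rule to it. Screening may last up to 10 weeks, so loss is conditional. It is, and the documents do not allow an estimate of how many participants are affected. But SAP 11.1 names RQLQ(S) and PFASQ in the list the rule serves, and the plan should not depend on a programmer ignoring it.

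The effect on the RQLQ(S) mean endpoint can also be disputed. Footnote 4 to Table 3 does not list RQLQ(S), and the same-as-above chain in SAP 14.1, read literally, ends at the EEU TNSS baseline. That is not a sensible covariate for a quality-of-life score. The instrument's own baseline is the natural reading.

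On the window, SAP 2.1 describes visit 10 as collecting symptoms before BPS, birch exposure is low by definition before BPS starts, and an early season shortens the gap after dose #2. These points limit the likely bias and make the largest shares extremes. They do not remove the conflict with footnote 26 or the label calling both baselines pre-treatment.

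**Conclusion.** All three faults hold on the text and should be fixed before the Part B analysis. The primary endpoint and the six hierarchical tests in SAP 8.2 are unaffected, taking the floor to apply to diary and questionnaire scores, as its placement suggests.

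- **Floor:** within-arm absolute change is wrong for every baseline below 1. The average size depends on a distribution the documents do not give.
- **Record rule:** the pre-treatment RQLQ(S) baseline is lost when visit 2 to dose #1 is shorter than about 3 weeks, or about 4 weeks if an oak challenge takes out a questionnaire day. Longer intervals are safe.
- **Window:** the share of days after dose #2 runs from 0% to 75%, depending on dosing date and diary length. The probable bias in change from pre-season baseline is toward no difference. Its size depends on a drug effect before BPS for which the documents give no figure.

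**What to change.** Change three sentences in SAP 11.1. No new data are needed.

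1. Use the observed baseline for absolute change and as covariate. Apply max(baseline, 1) only as the denominator of percent change.
2. Limit the three-record rule to daily instruments. Set a separate, lower minimum for RQLQ(S) and PFASQ, for example 1 record. State whether the dosing-day record counts and what is used if none qualifies. A single record is a noisier baseline, so the exact minimum is a judgement.
3. Reconcile the pre-season window with footnote 26 by ending the averaging before dose #2, or before local BPS start if that comes first.

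Item 3 costs some pre-season records. Where visit 10 is merged into an EEU visit, 7, 14 or 21 pre-dose days leave 0, 1 or 2 RQLQ(S) records, so item 2 must be changed with it. The corrected baseline is still not drug-free. With the protocol half-lives of 26.9, 34.0 and 35.1 days, 2^(-t/half-life) leaves 11% to 19% of dose #1 at 84 days and 2% to 5% at nominal day 155 (154 days later). The change from pre-treatment baseline, already planned, remains the drug-free comparison.

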11.3. Data for Non-Efficacy Endpoints

Missing data will not be imputed in listings.

Adverse event

If the intensity of a TEAE is missing, it will be classified as "severe" in the frequency tables by intensity of TEAEs. If the assessment of relationship of a TEAE to the investigational product is missing, it will be classified as related to the investigational product.

Adverse event start date

AE start date will be used for AE classification and analysis of AESIs. If AE start date is not complete, then the character variable will keep the original incomplete date, the numerical date variable will be imputed, and an imputation flag will be used to indicate which date component is missing.

If AE start day is missing, and AE start month and year are not missing: If AE start year is the same as first dose year and AE start month is the same as first dose month, then AE start day will be imputed using the day of first dose. If this leads to a date after the AE end date, AE end date will be used instead. If AE start month different from first dose month, AE start day will be imputed using the first day of the month. If this leads to a date before informed consent date, the informed consent date will be used. Imputation flag is 'D'.

If AE start month is missing, and AE start year is not missing: If AE start year is before the first dose year, the informed consent day and month will be used. If AE start year is the same as first dose year, the first dose day and month will be used. If this leads to a date after AE end date, AE end date will be used instead. If AE start year is after the first dose year, January 1st will be used. Imputation flag is 'M'.

If AE start year is missing: The date of first dose will be used. If this leads to a date after the AE end date, AE end date will be used instead. Imputation flag is 'Y'.

Adverse event end date

The general recommendation is not to impute AE end date. However, since AE end date will be used for AE start date imputation, to carry through the logic for programming, the following intermediate step will be used. Afterwards, only the original character/numeric date recorded in CRF will be kept in the final analysis dataset.

If AE end day is missing, and AE end month and year are not missing: AE end date will be imputed using the last day of the month. If this leads to a date after EOS follow up date, the end of follow up date will be used instead.

If AE end month is missing, and AE end year is not missing: AE end date will be imputed using December 31st as the day and month. If this leads to a date after EOS follow up date, the end of follow up date will be used instead.

If AE end year is missing: AE end date will be imputed using end of follow up date.

Medication start and end date missing

To determine whether a medication is prior medication or concomitant medication or both, the missing medication start date is estimated as early as possible, and the missing medication end date is estimated as late as possible. If the medication start date is missing, the onset day will not be calculated in medication listing.

Prior medication start date

If start day is missing, and start month and year are not missing: the start day will be imputed using the first day of the month. Imputation flag is 'D'.

If start month is missing, and start year is not missing: the day and month will be imputed using January 1st. Imputation flag is 'M'.

If start year is missing: the start date will be imputed using 2 years before informed consent date. Imputation flag is 'Y'.

A special note: for start date with year missing, the general principle is not to impute. However, to simplify the programming flow, the imputation is proposed to align with protocol which specifies to collect up to 2 years prior medication. Since the start date of prior medication will not be used in any analysis, the rule will not impact the analysis result.

Prior medication end date

If end day is missing, and end month and year are not missing: the end date will be imputed using the last day of the month. If this leads to a date on or after first dose intake date, the first dose intake date – 1 will be used. Imputation flag is 'D'.

If end month is missing, and end year is not missing: the end date will be imputed using December 31st as the day and month. If this leads to a date on or after first dose intake date, the first dose intake date -1 will be used instead. Imputation flag is 'M'.

If end year is missing: the end date will be imputed using the first dose intake date -1. Imputation flag is 'Y'.

Concomitant medication start date

The imputation rule for concomitant medication start date is the same as prior medication start date.

Concomitant medication end date

If end day is missing, and end month and year are not missing: the end date will be imputed using the last day of the month. If this leads to a date after EOS follow up date, the end of follow up date will be used. Imputation flag is 'D'.

If end month is missing, and end year is not missing: the end date will be imputed using December 31st as the day and month. If this leads to a date after EOS follow up date, the end of follow up date will be used instead. Imputation flag is 'M'.

If end year is missing: the end date will be imputed using the end of follow up date. Imputation flag is 'Y'.

Medication coding

Medications whose ATC level 4 cannot be coded will be summarized by setting ATC4=ATC2 in the table programs. However, these uncoded ATC level 4 records still need to be confirmed with study data manager and study medical director.

PCSV

Subjects who had post-baseline PCSV but missing baseline value will be regarded as having treatment-emergent PCSV.

11.4. Assignment of Data to Visit Windows and Unscheduled Assessments

Unscheduled Assessments

Data analyzed by-visit-analysis (including efficacy, laboratory data, vital sign, ADA) will be summarized by the study scheduled visits described in the "Schedule of Events" of study protocol and SAP.

The analysis visit windows are created per study Schedule of Events (SOE) table for each parameter and will be applied if the data from study scheduled visits are unavailable. The following general rules will be applied to unscheduled visit and/or early termination (ET) visit mapping for each parameter.

- 1. If ET visit falls in an analysis window which already has non-missing observed value of this parameter from the scheduled visit, ET will be mapped to the next scheduled visit in the same part.
- 2. If both ET visit and unscheduled visit of the same parameter are available in the same analysis visit window, only ET visit will be mapped.
- 3. If multiple unscheduled visits of the same parameter are available in the same analysis visit window, the unscheduled visits will be mapped using the following rules:
 - a. The closest unscheduled visit from the target day will be selected.
 - b. If the distance is a tie, the unscheduled visit after the target day of the scheduled visit will be used.
 - c. If multiple unscheduled visits exist on the same day, the first unscheduled visit will be used.
- 4. If mapping distance is greater than 6 weeks, the unscheduled visit will not be mapped.

Unscheduled visits and ET visit will be mapped per the following analysis visit windows for Part A and Part B based on the study day/visit of each parameter, respectively.

- 1. Part A visit window: All data collected after the last out-of-season EEU visit and/or the Visit 10 (whichever is later) will not be used for Part A analysis.
- 2. Part B visit window: All data not in Part A visit window will be included in Part B visit window.

Table 4: Analysis Visit Window for Safety and Laboratory Testings

	Visit	Tangat		, Physical nation	Hematology,	Drug	
Part	from SOE	Target Study Day ¹	Allergic to Oak ²	Not Allergic to Oak ²	Blood chemistry	Concentration sample	ADA sample
	Baseline	<=1			<=1		<=1
	Visit 6	29	[2, 33]	[2, 43]	[2, 43]	[2, 43]	-
Part	Visit 7	36	[34, 47]	-	-	-	-
Α	Visit 8	57	[48, 61]	[44, 61]	[44, 61]	[44, 61]	-
	Visit 9	85	>=	62	>=62	>=62	>=2
	Visit 10 ³	Before the dose in Part B	All data aft	er the last ou	t-of-season EEU	visit and before th	e dose in Part B.
	Visit 11	~0 to 3 weeks prior to start of BPS			-		
Part B	Visit 13	During peak BPS	Ass	essment dur	ing the actual l	ocal BPS	-
	Visit 14	At the end of BPS	Assess	ment at the	end of the actu	al local BPS	-
	Visit 15 (EOS)	After BPS		nt after the ocal BPS	-	Assessment after the actual local BPS	Assessment after the actual local BPS

^[1] Study days in Part A are calculated from the day of 1st injection. Study day = (date of assessment − 1st injection date + 1) when date of assessment ≥1st injection date; otherwise, study day = (date of assessment − 1st injection date). If subject never received any dose of study drug, randomization date will be used in the place of 1st injection date. Visit timeframes in Part B (visits 10 to 15) may vary based on the timing and duration of the anticipated BPS.

Mapping rule for EEU symptom scores

All symptom scores collected in EEU will be mapped to nominal time due to an allowed window to answer the questionnaire.

^[2] The visit mapping rule for participants who are allergic to oak is slightly different with participants who are not allergic to oak for vital sign and physical examination.

^[3] If visit 10 is combined with visit 6, visit 8, or visit 9, there will be no assessment for visit 10 and no titrated SPT in unscheduled visit will be mapped to visit 10. If visit 10 is combined with visit 7, the unscheduled titrated SPT collected after the last out-of-season EEU visit and before the dose in Part B will be mapped to visit 10.

Table 5: Summary of EEU Nominal and Derived Times

EEU Time	Analysis Timepoint	Nominal Time	Window for Derived Time ^{1,2}
EEU Qualification	-1	-0:15	<-0:10
Pre-EEU	0	0:00	[-0:10, 0:10)
	1	0:20	[0:10, 0:30)
	2	0:40	[0:30, 0:50)
In EEU	3	1:00	[0:50, 1:10)
0 to <2 hours	4	1:20	[1:10, 1:30)
	5	1:40	[1:30, 1:50)
	6	2:00	[1:50, 2:10)
	7	2:20	[2:10, 2:30)
	8	2:40	[2:30, 2:50)
	9	3:00	[2:50, 3:10)
	10	3:20	[3:10, 3:30)
	11	3:40	[3:30, 3:50)
In EEU	12	4:00	[3:50, 4:10)
2-6 hours ³	13	4:20	[4:10, 4:30)
	14	4:40	[4:30, 4:50)
	15	5:00	[4:50, 5:10)
	16	5:20	[5:10, 5:30)
	17	5:40	[5:30, 5:50)
	18	6:00	[5:50, 6:10)

^[1] Derived time = actual assessment calendar time (hh:mm) – EEU entry calendar time (hh:mm) for Cliantha site, as well as the EEU qualification and pre-EEU measurement in Kingston site. Derived time = actual assessment calendar time (hh:mm) – EEU entry calendar time (hh:mm)-15 min for Kingston Site (15 mins for Kingston site to prepare the pollen exposure after participants enter the EEU).

